3.1 Description of Study Design

This study is a randomized, double-blind, placebo-controlled, multicenter trial of non-standardized glycerinated German cockroach (*Blattella germanica*) allergenic extract or placebo treatment administered by subcutaneous injection.

Participants will be randomized to 1 of 2 treatment groups in a ratio of 1:1:

1. German cockroach allergenic extract administered by subcutaneous injection.
2. Placebo administered by subcutaneous injection.

Protocol ICAC-28 will enroll eighty 8 to 17-year-old cockroach sensitive children with asthma with a positive cockroach Nasal Allergen Challenge (NAC) before randomization.

The intended maintenance dose of German cockroach allergenic extract is ≈ 6 mcg of Bla g 2. The study will be based on a treatment schedule with German cockroach allergenic extract or placebo for 12 months.

There will be a Screening phase to determine eligibility, including a positive IgE and skin test to German cockroach. If asthma control parameters are not met, participants will begin a run-in period, during which participants' asthma medications will be adjusted for up to 4 months to achieve symptom control before completing an initial NAC procedure. Eligible participants with a positive NAC will then be randomized to one of the two treatment arms and receive their first injection. Up to 2 doses of SCIT will be given weekly during dose escalation, separated by a minimum of 2 days. Dose escalation can be delayed at any point for systemic or local reactions, although to continue to maintenance each participant will need to reach the minimum maintenance dose in a maximum of 40 weeks (see Appendix B: Study Restrictions Due to COVID-19). Once the maintenance dose is achieved, participants will receive two additional maintenance level-doses (for a total of three maintenance level-doses) spaced approximately 2 weeks apart, followed by maintenance injections every 4 weeks for the remainder of the treatment period.

At Randomization and every 2 months during treatment, an asthma Evaluation and Management (E&M) process will occur where participants' asthma medication regimen will be adjusted based on symptoms, albuterol/levalbuterol use, FEV₁, recent exacerbations, and their current level of therapy.

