6.7 Premature Discontinuation of Investigational Agent

Participants who are unable to reach the minimum maintenance dose by 40 weeks following the start of dose escalation will be unable to proceed to the maintenance period and will have their study therapy discontinued (see Section 11.2.1 Discontinuation of Study Therapy; see Appendix B Study Restrictions Due to COVID-19).

Study therapy may be prematurely discontinued for any participant for any of the reasons identified in Section 11.2.1 Discontinuation of Study Therapy. Study therapy may also be prematurely discontinued for any participant if the study clinician believes that the study treatment is no longer in the best interest of the participant. Participants whose therapy is prematurely discontinued will be followed when possible for the duration of the study and seen for all remaining visits except Injection Visits.

7 Other Medications

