8.6.2 Maintenance Visits

Participants who have completed dose escalation will receive one injection of investigational agent every 2 weeks for 3 doses, followed by maintenance injections every 4 weeks to complete a maximum of 12 months of treatment.

During the maintenance phase, a urine pregnancy test will be performed at the E&M visits (every two months) on all female participants that have reached menarche.

Dosing modifications as a result of reaction or lapse in dosing for the three, initial, maintenance-level injections, planned at two week intervals, are detailed in the MOP for Protocol ICAC-28. Additionally, dosing modifications as a result of reaction or lapse in dosing for the subsequent maintenance level injections planned at four-week intervals are detailed in the MOP for Protocol ICAC-28.

Participants will be instructed to immediately report any severe sign or symptom possibly related to the subcutaneous administration of the investigational agent and to contact the study site when they need medical advice. At each visit, participants will be queried regarding any delayed reactions or side effects experienced. For those participants with asthma, exacerbations will be handled through an approach consistent with standard clinical practice as described in the Protocol ICAC-28 MOP.

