13.4 Analysis Plan

13.4.1 Analysis Populations

The following groups of participants will define samples for endpoint analysis:

- Modified Intent-to-treat (ITT) sample: All participants who are randomized, received at least one dose of study treatment, and receive at least one dose during the 12-month NAC. Participants will be analyzed according to the treatment arm to which they were randomized, regardless of the medication they actually received.
- Safety sample: All participants who sign consent and undergo study procedures at Screening. Participants will be analyzed according to the medication they actually received, regardless of the

treatment arm to which they were randomized. Non-treatment-emergent adverse events (e.g., any adverse event that occurs before the first injection) will be summarized in all participants who are enrolled, while treatment-emergent adverse events (e.g., any adverse event that occurs on or after the first injection) will be summarized in the safety sample.

- Per-protocol (PP) sample: All participants who are randomized, are escalated to 0.4 mL of the 1:10 maintenance dose, and receive at least 66% of expected doses of maintenance.

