5. ANALYSIS SAMPLES

[ICH E3: 11.4.2.6](#); [ICH E9: 5.2](#)

The following groups of participants will define samples for endpoint analysis:

- **Modified Intent-to-treat (ITT) sample:** All participants who are randomized, received at least one dose of study treatment, and receive at least one dose during the 12-month NAC. Participants will be analyzed according to the treatment arm to which they were randomized, regardless of the medication they actually received.
- **Safety sample:** All participants who sign consent and undergo study procedures at Screening. Participants will be analyzed according to the medication they actually received, regardless of the treatment arm to which they were randomized. Non-treatment-emergent adverse events (e.g., any adverse event that occurs before the first injection) will be summarized in all participants who are enrolled, while treatment-emergent adverse events (e.g., any adverse event that occurs on or after the first injection) will be summarized in the safety sample.
- **Per-protocol (PP) sample:** All participants who are randomized, are escalated to at least 0.4 mL of the 1:10 maintenance dose, and receive at least 3 doses of maintenance SCIT/placebo.

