7.3. Measures of Treatment Compliance

ICH E3: 9.4.8

Subjects are intended to escalate to at least 0.4 mL of the 1:10 maintenance dose and continue the maintenance dose regimen every 4 weeks up to 12 months after the beginning of therapy per the protocol (section 8.6.2). Dose escalation takes a minimum of 26 weeks and can take up to a maximum of 40 weeks. Thus, the minimum number of maintenance doses remaining in the 12-month study would be 3 and the maximum would be 6.

Treatment compliance during the maintenance period will be summarized separately for each treatment arm and listed.

Treatment compliance during the maintenance period will be calculated as:

$$\% \text{ Compliance} = \frac{\# \text{ of actual maintenance doses}}{\# \text{ of expected maintenance doses}} \times 100$$

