12. CHANGES TO THE ANALYSES PLANNED IN THE PROTOCOL

ICH E3: 9.8

The protocol describes the Per Protocol analysis population to be “All participants who are randomized, are escalated to at least 0.4 mL of the 1:10 maintenance dose and receive at least 66% of expected doses of maintenance.”

This analysis plan has changed the definition of the Per Protocol analysis population to be “All participants who are randomized, are escalated to at least 0.4 mL of the 1:10 maintenance dose and receive at least 3 doses of maintenance.” This change was made to simplify the definition due to the pause in immunotherapy caused by the COVID-19 pandemic.

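### SAP 7.3 undercounts scheduled maintenance doses, so the flat 3-dose per-protocol floor is only 30–43% of schedule after a normal 16–26 week escalation

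*SAP*

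**What the plan says.** SAP 5 defines the per-protocol sample as randomized participants who "are escalated to at least 0.4 mL of the 1:10 maintenance dose, and receive at least 3 doses of maintenance SCIT/placebo". Protocol 13.4.1 instead requires that they "receive at least 66% of expected doses of maintenance". SAP 12 declares the change and explains it: "This change was made to simplify the definition due to the pause in immunotherapy caused by the COVID-19 pandemic".

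SAP 7.3, on treatment compliance, cites Protocol 8.6.2 and states: "Dose escalation takes a minimum of 26 weeks and can take up to a maximum of 40 weeks". It concludes: "Thus, the minimum number of maintenance doses remaining in the 12-month study would be 3 and the maximum would be 6". Compliance is then actual over expected maintenance doses, times 100.

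Protocol 8.6.2 describes maintenance as "one injection of investigational agent every 2 weeks for 3 doses, followed by maintenance injections every 4 weeks", for at most 12 months of treatment. Protocol 3.1 gives the same pattern but counts the dose that reaches maintenance as the first of the three. Footnote 5 in Protocol Appendix A, repeated in SAP 14.3, gives 16–26 weeks as the normal length of escalation and 40 weeks as the limit.

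Participants who stop therapy early stay in follow-up where possible and are "seen for all remaining visits except Injection Visits" (Protocol 6.7; also 11.4). SAP 8.2 and 14.1 name the per-protocol population beside mITT for the primary endpoint.

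**The concern.** SAP 7.3 describes the schedule differently from the protocol section it cites and from the SAP's own schedule of events. If more doses are scheduled than it says, a floor of 3 is a weaker requirement than it appears beside a stated range of 3 to 6.

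The floor carries no condition on timing, on share of schedule, or on time since the last injection. A participant could receive the three opening doses, stop, return for the 12-month challenge and count as per-protocol. Readers will take the per-protocol result as the effect in children treated broadly as planned. Including children long off treatment would blur that meaning. Permitted reasons for stopping include grade 3–4 systemic reactions and related serious adverse events (Protocol 11.2.1). These could be more common on active extract, though the documents give no rate.

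**Working it through.** **Inputs.** W is the week in which escalation ends, for a participant without a COVID-19 pause.

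- W = 16 to 26 normally, 40 at most (Protocol Appendix A; SAP 14.3).
- Three doses 2 weeks apart, then every 4 weeks (Protocol 3.1, 8.6.2).
- The challenge is taken at week 52. Appendix A marks no injection at the 12-Month Visit, so doses are counted before week 52.

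**Check on 16 weeks.** Doses 1–20 at up to two per week take 20/2 = 10 weeks (Protocol 3.1, 8.11). Doses 21–26, at least 5 days apart (8.6.1), take about 6 weeks at one per week. 10 + 6 = 16.

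**The SAP's figure.** With 4-weekly doses only:

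- W = 40: (52 − 40)/4 = 3
- W = 26: (52 − 26)/4 = 6.5, so 6

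This reproduces 3 to 6, but only by omitting the 2-weekly doses and taking 26 weeks as the shortest escalation.

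**The protocol schedule.**

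3.1 reading (doses at W, W+2, W+4, then every 4 weeks):

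- W = 16: 16, 18, 20, 24, 28, 32, 36, 40, 44, 48 = 10
- W = 26: 26, 28, 30, 34, 38, 42, 46, 50 = 8
- W = 40: 40, 42, 44, 48 = 4

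8.6.2 reading (doses at W+2, W+4, W+6, then every 4 weeks):

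- W = 16: 18, 20, 22, 26, 30, 34, 38, 42, 46, 50 = 10
- W = 26: 28, 30, 32, 36, 40, 44, 48 = 7
- W = 40: 42, 44, 46, 50 = 4

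Allowing an injection at week 52 adds at most one dose. Even on the SAP's own 26 and 40 weeks the counts are 7 or 8 and 4, not 6 and 3.

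**What a floor of 3 means.** Share = 3/n. The 66% requirement is 0.66n rounded up. The gap is 52 minus the week of the third dose.

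| W | Scheduled n | 3/n | 66% needs | Gap after third dose |
|---|---|---|---|---|
| 16 | 10 | 30% | 7 (6.6) | 32 or 30 weeks |
| 26 | 8 or 7 | 38% or 43% | 6 (5.28) or 5 (4.62) | 22 or 20 weeks |
| 40 | 4 | 75% | 3 (2.64) | 8 or 6 weeks |

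On the SAP's own maximum of 6, three doses are 50%, and 66% would need 4 (0.66 × 6 = 3.96).

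**If only 4-weekly doses count.** The SAP does not say whether the 2-weekly doses are maintenance. Without them the schedule holds 7 doses (W = 16), 5 or 4 (W = 26) and 1 (W = 40), which is not 3 to 6 either. The third 4-weekly dose falls at W+16 or W+18, so a fully adherent participant who ends escalation after week 35 (or 33) cannot reach 3 before week 52.

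**The case against.** **The 26-week figure has some basis.** Protocol 8.6.1 speaks of weekly injections, and Table 8.6.1 has 26 numbered doses from Dose 1. That explains 26 weeks as a typical length. It does not make it a minimum, since Protocol 3.1 and 8.11 allow two injections a week and both schedules say 16–26.

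**The dose counts are not fixed protocol limits.** The 40-week limit in Protocol 3.1, 6.7 and 8.6.1 applies to Dose 20, the minimum maintenance dose. A child reaching Dose 20 at week 40 and then taking Doses 21–26 weekly would end at week 46 and have 3 doses left (46, 48, 50). However, 8.11 says escalation itself must finish within 40 weeks. A child held at Dose 20 from week 10 would have up to 12. This stands as a caution: the counts apply to the stated W.

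**The longest gap is a corner case.** A reader might infer that per-protocol children would typically be untreated for 32 weeks. The documents do not support that. It needs the fastest normal escalation, stopping straight after the third dose, a completed challenge, and the 2-weekly doses counting. On the 4-weekly reading with W = 16, the third such dose falls at week 32 or 34, leaving 18–20 weeks. The admission problem and the exclusion of slow escalators belong to different readings and cannot both occur.

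**The compliance table need not be wrong.** A reader might infer that full adherence will print above 100%. That follows only if 3 to 6 is used as the denominator (10/6 = 167%, 7/6 = 117%). The formula says expected doses without fixing them at those values, and Protocol 6.5 tracks expected and completed visits.

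**The change is declared.** SAP 12 quotes both definitions and gives a reason, and a minimum-exposure floor is a legitimate choice. But the COVID-19 reason does not explain applying it to children who were never interrupted, whom SAP 8.5 already separates.

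**Conclusion.** The SAP 7.3 statement is wrong and should be corrected. Uninterrupted participants are scheduled for about 10 maintenance-level doses after a 16-week escalation, 7 or 8 after 26 weeks and 4 after 40 weeks. The flat floor of 3 is therefore 30–43% of schedule for normal 16–26 week escalators and agrees with the protocol's 66% only for the slowest. It can admit participants last injected 20–22 weeks before the challenge after a 26-week escalation, and 30–32 weeks at the extreme.

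This rests on a week-52 challenge, no injection at that visit, no COVID-19 pause, and the 2-weekly doses counting as maintenance. The documents do not say how many children stop early or how quickly any effect wanes, so the effect on the per-protocol estimate cannot be sized.

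The point does not reach the mITT analysis. Nor do the documents show that the floor of 3 was taken from the minimum of 3 in SAP 7.3; the weakness follows from the floor itself.

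**What to change.** **SAP 7.3.** Delete the sentences giving a 26-week minimum and 3 to 6 doses. Replace them with:

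> The three 2-weekly doses count as maintenance doses. Expected maintenance doses are counted for each participant from the protocol schedule up to the 12-month visit, omitting weeks of COVID-19 suspension and weeks of protocol-required re-escalation. This count is the denominator for percent compliance.

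Both exclusions are needed. Interrupted participants had to re-escalate (Protocol Appendix B; SAP 8.1.2), so leaving out only the closure weeks could fail a fully adherent child.

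**SAP 5 and 12.** Apply the protocol's 66% rule on that denominator. If the flat floor of 3 is kept for COVID-interrupted participants, apply 66% to uninterrupted participants and report the per-protocol result under both definitions.

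**Cost.** SAP wording, settled before database lock. Expected and completed injection visits are already monitored (Protocol 6.5), and SAP 7.3 already needs an expected count. Identifying re-escalation weeks takes some derivation under the manual's dosing rules. The per-protocol set may be smaller, by an unknown amount. The 1:10 wording of the dose floor and the empty exposure section (SAP 9.2) are separate minor points.

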6. STUDY SUBJECTS

6.1. Disposition of Subjects

[ICH E3: 10.1](#)

The disposition of all enrolled subjects will be summarized in tables and listed. The following disposition information will be summarized:

- The number of participants screened.
- Among screened participants:
 - The number and percentage of participants who failed Screening, including those that attended the Screening visit but did not meet the inclusion/exclusion criteria.
 - The number and percentage of participants in the mITT sample.
 - The number and percentage of participants in the safety sample.
 - The number and percentage of participants in the PP sample.
- Among participants in the mITT sample and grouped by treatment arm:
 - The number and percentage of participants in the safety sample.
 - The number and percentage of participants in the PP sample.

National Institute of Allergy and Infectious Diseases
{Statistical Analysis Plan - Protocol #}

- The number and percentage of participants who completed the 12 month NAC.
- The number and percentage of participants who withdrew during the study due to:
 - Withdrawal by participant
 - Lost to follow-up
 - Death
 - Pregnancy
 - Physician decision
 - Participant experienced an anaphylactic reaction to study drug injection
 - Participant was diagnosed with an exclusionary malignancy
 - Participant acquired an opportunistic infection
 - Non-compliance with the study protocol
 - Participant refused protocol-mandated procedure at the Screening of Treatment Initiation Visit
 - Adverse Event
 - Other

A data listing of subject disposition will be provided for the mITT population.

6.2. Demographic and Other Baseline Characteristics

ICH E3: 11.2

Summary descriptive statistics for demographic and baseline characteristics will be summarized in the mITT population grouped by randomized treatment arm and overall.

Demographic data will include age at randomization, sex, race, ethnicity, and site.

Baseline will be defined as the last measurement prior to or on the day of randomization (beginning of Month 0). Baseline characteristics will include:

- Age
- Sex
- Race
- Caretaker completed high school
- Annual household income (<15k)
- CASI & CASI subscales
- Cockroach-specific IgE and IgG4
- NAC Responsive Dose

National Institute of Allergy and Infectious Diseases
{Statistical Analysis Plan - Protocol #}

Demographic and baseline characteristics for continuous variables will be summarized using the number of participants, mean, standard deviation, median, and first and third quartiles (as applicable). Demographic and baseline characteristics for qualitative or categorical variables will be summarized by the number and percentage of participants within each category. Demographic and baseline characteristics in the mITT sample will also be compared between treatment arms using T-tests, Wilcoxon Sign-Rank Tests, or Chi-Square Tests, as applicable.

A data listing of demographics, baseline characteristics, and medical history will be provided for the mITT sample. A data listing of any inclusion/exclusion criteria not met will also be provided for all screened participants as well as all participants in the mITT sample separately.

6.3. Prior and Concomitant Medications

Medications will be coded according to the World Health Organization (WHO) Drug Dictionary (version 2017.01). Medications reported on the CRF will be categorized for analysis as prior, concomitant, or after study treatment by comparing the medication start and stop dates with the first and last dose of study medication dates. Prior medications will have both the medication start and stop dates prior to the first dose of study medication date. After medications will have both the medication start and stop dates after the last dose of study medication date. All other medications will be classified as concomitant, indicating that use of the medication overlapped with use of the study medication by at least one day.

The number and percentage of subjects receiving prior, concomitant, and after medications will be presented overall and by medication class. When reporting the number of subjects receiving the medication, a subject will only be counted once if they ever received the medication within the medication class. Percentages will be based on the number of subjects in the analysis population.

7. STUDY OPERATIONS

7.1. Protocol Deviations

ICH E3: 10.2

Protocol deviations will be recorded on the protocol deviation electronic case report form (eCRF). Major protocol deviations will be identified by the DAIT Medical Monitor and study team prior to unblinding of treatment assignment and database freeze.

A data listing of all protocol deviations sorted by site and subject ID will be provided to the DAIT Medical Monitor and study team for the manual identification of major protocol deviations.

Following database freeze, a data listing will be provided for protocol. The listing will be sorted by site, treatment arm, and subject ID and will also include type of deviation, severity of the deviation (major or non-major), date of occurrence, and the reason for the deviation.

Protocol deviations will be summarized in tabular format by site and by type of deviation (including the major deviations listed above).

7.2. Randomization

The randomization schedule was generated by the DAIT NIAID Statistical and Clinical Coordinating Center (SACCC) and implemented in a validated system that was used by site personnel to automate the random assignment of treatment groups to study participants. The randomization scheme was reviewed and approved by a statistician at the DAIT SACCC and was not modified thereafter. Participants were randomized using a 1:1 ratio, stratified by site, of active (German cockroach extract) and control (placebo) participants.

7.3. Measures of Treatment Compliance

ICH E3: 9.4.8

Subjects are intended to escalate to at least 0.4 mL of the 1:10 maintenance dose and continue the maintenance dose regimen every 4 weeks up to 12 months after the beginning of therapy per the protocol (section 8.6.2). Dose escalation takes a minimum of 26 weeks and can take up to a maximum of 40 weeks. Thus, the minimum number of maintenance doses remaining in the 12-month study would be 3 and the maximum would be 6.

Treatment compliance during the maintenance period will be summarized separately for each treatment arm and listed.

Treatment compliance during the maintenance period will be calculated as:

$$\% \text{ Compliance} = \frac{\# \text{ of actual maintenance doses}}{\# \text{ of expected maintenance doses}} \times 100$$

